Problem Statement: Global competition and evolving healthcare needs in the 21st century have highlighted the limitations of traditional in-class learning methods. Generation Z students, with limited attention spans and a tendency to become easily bored by monotony and repetition, necessitate changes in conventional teaching methods. In nursing education, developing core skills such as problem-solving, creativity, collaboration, and media literacy is crucial to enhance learning outcomes and strengthen the educational process. These skills help students face challenges in both their careers and social lives. To actively engage nursing students and support critical thinking and life skills, a combination of teaching methods such as lectures, presentations, group discussions, problem-based learning, and role-playing should be employed. Pecha Kucha (PK) is an internationally recognized, innovative, visually-focused presentation technique used in educational settings. Derived from Japanese, meaning "chit chat," PK is a narrative and visualbased slide presentation method. Each presentation consists of 20 slides, shown for 20 seconds each, totaling 6 minutes and 40 seconds. PK allows for concise, fluid, and natural delivery of information. Its structured and time-limited nature enables presenters to communicate key information clearly without straying from the main topic. The "spirit" of Pecha Kucha lies in the harmonious use of strong visuals and carefully selected text. Effective presentations require highquality visuals or images aligned with content knowledge, the intended message, and the target audience. Each slide presents a single concept or idea with balanced information, enabling the presenter to convey content quickly and succinctly. The short, visually-oriented format facilitates active and attentive engagement from the audience. PK has been reported as an effective tool to support student learning outcomes and instructor objectives in health education compared to traditional PowerPoint methods.

The use of PK in nursing education has been studied in areas including knee replacement and nursing approaches, pathophysiology education, development of presentation skills, social anxiety and learning attitudes related to Human Papilloma Virus infection and vaccination, stoma care skills, and teaching vital signs skills. Similarly, Topal et al. and Bakcek et al. reported that PK positively affected student satisfaction. However, no studies have examined the impact of PK on ERAS education in nursing students. Recent advancements in surgical procedures and anesthesia techniques emphasize evidence-based patient care rather than traditional approaches. Enhanced Recovery After Surgery (ERAS) protocols, also known as Fast Track Surgery (FTS), aim to minimize physiological stress, optimize pain control, and accelerate postoperative recovery. Developed in 2001 by a consortium of five centers in Northern Europe for elective colon surgeries, ERAS protocols have since expanded to gynecologic oncology, urology, other gastrointestinal surgeries, orthopedic surgeries, and beyond. The ERAS Society was established in Stockholm in 2012 to formalize and disseminate these protocols. Although ERAS has become standard in many surgical fields, cardiovascular

applications began around 2019. ERAS requires interdisciplinary collaboration, including surgeons, nurses, anesthetists, physiotherapists, and dietitians. Nurses play a critical role in protocol implementation, patient education, and coordination of care. Studies indicate low awareness of ERAS among nurses: Çelebi & İlçe reported that 86.8% of nurses were unaware of ERAS, and 79.2% stated it was not applied in their clinics. Ongun & Ak found that 84.25% of nurses did not know about ERAS, 88.97% reported it was not applied in their workplaces, 99.21% did not follow any publications on ERAS, and 99.21% had not received ERAS training. Güzel & Yava noted low knowledge but high interest among nurses. Akpolat et al. applied escape room teaching for ERAS education, reporting improved student knowledge. Studentcentered methods have been shown to deliver information quickly, increase interaction, and enhance retention compared to traditional teaching. No studies have evaluated PK for cardiovascular ERAS education, representing a significant research gap. This study aims to assess PK's impact on nursing students' ERAS knowledge and attitudes towards evidence-based nursing.

Research Questions: 1. Does cardiovascular ERAS education delivered via Pecha Kucha improve students' theoretical knowledge? 2. Does cardiovascular ERAS education delivered via Pecha Kucha improve students' attitudes toward evidence-based nursing? **Study Objectives:** 1. Determine differences in cardiovascular ERAS knowledge levels between students educated via Pecha Kucha versus traditional PowerPoint. 2. Assess differences in attitudes toward evidence-based nursing between these groups.

Study Design: A randomized controlled experimental design with pre- and post-test measurements will be employed, following CONSORT guidelines. The study protocol will be registered in ClinicalTrials.gov prior to commencement. **Study Location and Period:** Lokman Hekim University, Faculty of Health Sciences, Nursing Department, May 15, 2026 – May 15, 2027.

Population and Sample: The population consists of 71 second-year nursing students enrolled in the Surgical Nursing course. Participants will be divided into intervention (PK) and control (PowerPoint) groups using block randomization based on pre-test scores (≤ 60 / > 60) and gender (female/male). Randomization will be performed via <https://www.randomizer.org/> (Bacanlı & Uçar, 2013).

Data Collection Tools:

1. Student Demographic Form: Age, gender, prior ERAS knowledge, and satisfaction (5 questions).
2. Cardiovascular ERAS Knowledge Test: 50 multiple-choice and 50 openended questions, totaling 100 points.
3. Evidence-Based Nursing Attitude Scale (KDHYTÖ): 15-item Likert scale, 3 subscales: beliefs and expectations, implementation intention, emotions.

Data Collection: Pre-test conducted one week prior to lecture; block randomization follows; intervention delivered: PK for intervention group, traditional PowerPoint for control. Post-test and delayed post-test conducted to assess retention.

Data Analysis: IBM SPSS 26. Descriptive statistics, t-tests, Mann-Whitney U, paired t-tests, Wilcoxon, Chisquare. Significance at $p < 0.05$.

Ethical Considerations: Approved by Lokman Hekim University Scientific Research Ethics Committee and Clinical Research Ethics Committee (Ethics Committee Approval: Decision No. 2025/332, Meeting No. 2025/14, dated December 30, 2025). Informed consent obtained. Data confidential, used for research only, stored securely, and shared only among researchers.

References:

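### The stratification cut at a pre-test score of 60 has no stated basis and may give little protection against chance baseline imbalance; the observed scores, in hand before allocation, would do better

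*Protocol*

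**What the plan says.** All references are to the protocol.

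- **Population and Sample.** "The population consists of 71 second-year nursing students enrolled in the Surgical Nursing course". They are split into a Pecha Kucha and a PowerPoint group "using block randomization based on pre-test scores (≤ 60 / > 60) and gender (female/male". Crossing the two factors gives four strata. No rationale, pilot result or expected pre-test mean accompanies the figure of 60.
- **Data Collection Tools.** The knowledge test has "50 multiple-choice and 50 openended questions, totaling 100 points". A separate form records "Age, gender, prior ERAS knowledge, and satisfaction (5 questions"; no expected level of prior knowledge is stated.
- **Data Collection.** "Pre-test conducted one week prior to lecture; block randomization follows". Every pre-test score therefore exists before anyone is allocated.
- **Problem Statement.** Two cited surveys report that "86.8% of nurses were unaware of ERAS" and that "84.25% of nurses did not know about ERAS"; in the second, "99.21% had not received ERAS training".

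**The concern.** Stratifying on a baseline score helps only if the cut divides the sample into groups of useful size. If nearly everyone falls on one side, the score factor is almost constant. The allocation is then balanced on gender, while pre-test knowledge is left to chance.

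Three features of the protocol point towards low scores: the pre-test precedes the lecture, half the questions are open-ended and so hard to guess, and the protocol's own case for teaching the topic is that nurses know little about it. With only 71 students, chance imbalance in the baseline value of the main outcome is not trivial. It passes to the post-test in proportion to the pre/post correlation. The documents give no correlation; at an assumed 0.5, a 0.3 SD baseline gap becomes 0.5 × 0.3 = 0.15 SD at post-test.

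**Working it through.** The protocol states no pre-test distribution and no balance figure, so there is nothing to reproduce. The check asks how the cut at 60 behaves over a range of possible distributions.

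**Inputs from the protocol:** 71 students; cut ≤ 60 / > 60 crossed with gender; 50 multiple-choice and 50 open-ended questions for 100 points; pre-test before randomisation.

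**Assumptions:** one point per question; four or five options per multiple-choice question; 1:1 allocation (36/35); 20% men; blocks of four; normally distributed scores with SD 15 (SD 10 as a variant) and means from 25 to 60.

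**Step 1: what 60 points demands.** A student who knows a share k of the content and guesses the remaining multiple-choice questions with success probability g expects 50[k + (1 − k)g] + 50k points.
- g = 1/4: 12.5 + 87.5k = 60, so k = 0.543.
- g = 1/5: 10 + 90k = 60, so k = 0.556.

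A perfect multiple-choice half yields only 50, so passing 60 needs real open-ended knowledge.

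**Step 2: imbalance with no score stratification.** The SD of the between-arm difference in mean pre-test, in units of the pre-test SD, is √(1/36 + 1/35) = 0.237. Hence P(|difference| > 0.3 SD) = 2[1 − Φ(0.3/0.237)] ≈ 0.21.

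**Step 3: number above 60.** The expected count is 71 × [1 − Φ((60 − mean)/SD)]. For mean 35 and SD 15 this is 71 × [1 − Φ(1.67)] = 71 × 0.048 = 3.4.

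**Step 4: simulated chance of a baseline difference above 0.3 SD (SD 15).**

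| Pre-test mean | Expected number above 60 | Cut at 60 | Observed median | Ranked blocks of four within gender |
|---|---|---|---|---|
| 25 | 0.7 | 21% | about 5% | about 0% |
| 35 | 3.4 | 18% | about 5% | about 0% |
| 45 | 11.3 | 11% | about 5% | about 0% |
| 50 | 17.9 | 8% | about 5% | about 0% |
| 60 | 35.5 | 5% | about 5% | about 0% |

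Repeat simulations differ by about one percentage point. The average baseline difference was about zero in every scenario where it was recorded.

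**Step 5: variant with SD 10.** The expected number above 60 is 0.4 at mean 35, 4.7 at mean 45 and 11.3 at mean 50. The chance of a difference above 0.3 SD with the cut at 60 is then 22%, 17% and 12%. The first is the unstratified figure within simulation error.

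**The case against.** The strongest objection is that the harm depends on a distribution the documents do not give. A reader might infer that nearly all students will land in one stratum. The protocol does not support that:

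- The survey figures describe awareness of ERAS among practising nurses, not students' scores on a test.
- That the students are untaught is an inference from the timing. They are enrolled in Surgical Nursing, and the form asks about prior ERAS knowledge.
- At a mean of 50 or more, between 11 and 36 of the 71 would exceed 60 under the assumptions above, and the cut does useful work.
- Gender still splits the lower score group, so even an empty upper level leaves two strata.

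A reader might also infer that randomisation fails or that the comparison is biased. It does not and is not. Allocation is balanced in expectation whatever the cut, an empty stratum adds no bias, and the standard error of an unadjusted test already allows for chance imbalance. Even with no score stratification, about 79% of allocations fall within 0.3 SD.

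Nor can it be said that the analysis will ignore the pre-test. Data Analysis is a short list of tests without a baseline-adjusted model, but a statistical analysis plan that is not shown may add one. Adjustment would remove much of the consequence of an imbalance. Finally, if scores are tightly bunched, 0.3 SD is few points: pure guessing on 50 four-option questions has SD √(50 × 0.25 × 0.75) ≈ 3.1, so 0.3 SD ≈ 0.9 points.

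All of this stands, and it limits the claim to a possible loss of balance and precision. It does not rescue the figure of 60. Within simulation error the observed median was no worse at any mean tried, and it merely equals 60 when 60 happens to be the median. A fixed cut offers no compensating advantage here, because the scores are known before allocation.

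**Conclusion.** The point holds as an avoidable weakness in the design, not as a flaw in validity. The cut of 60 is fixed without a stated basis, and the protocol's own description of the test and topic makes a thin upper group plausible. The chance of a baseline gap above 0.3 SD with that cut runs from about 21% if the mean is near 25, where the score factor does nothing, to about 5% if the mean is near 60. Using the observed scores holds it at about 5% (median) or about 0% (ranked blocks) wherever the mean lies.

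These sizes rest on assumed normal scores, SD, gender share, block size and 1:1 allocation. Confidence is moderate: the direction is secure, but the size of the gain depends on the unknown pre-test distribution.

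**What to change.** In Population and Sample, replace the fixed cut by one of the following, both still within gender:

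- stratify at the observed median pre-test score of the cohort, with scores equal to the median assigned to the lower group; or
- preferably, sort students by pre-test score within gender and randomise within consecutive blocks of four.

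In either case, allocate everyone in a single run after all pre-tests are marked, so that small blocks make no assignment predictable. If the sponsor prefers to keep 60, the protocol should justify it, for example from pilot scores on the same test.

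The cost is a sentence or two before the study starts. No extra data are needed: the pre-tests must be marked before allocation under the present plan as well.

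### The research questions name no comparator while the objectives do, and the listed tests are within-arm or leave out the pre-test score; a baseline-adjusted PK versus PowerPoint difference would settle both at no cost

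*Protocol*

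**What the plan says.** Under Research Questions, the Protocol asks "Does cardiovascular ERAS education delivered via Pecha Kucha improve students' theoretical knowledge" and "Does cardiovascular ERAS education delivered via Pecha Kucha improve students' attitudes toward evidence-based nursing". Neither question mentions PowerPoint.

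Under Study Objectives, both aims are comparative: "Determine differences in cardiovascular ERAS knowledge levels between students educated via Pecha Kucha versus traditional PowerPoint" and "Assess differences in attitudes toward evidence-based nursing between these groups".

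Under Study Design: "A randomized controlled experimental design with pre- and post-test measurements will be employed, following CONSORT guidelines". Data Collection adds a third measurement: "Post-test and delayed post-test conducted to assess retention".

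Population and Sample gives a class of 71 and stratifies the allocation by pre-test score (cut at 60) and gender.

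Data Analysis lists "Descriptive statistics, t-tests, Mann-Whitney U, paired t-tests, Wilcoxon, Chisquare" at the 0.05 level. The list holds two-sample tests and paired tests. It contains no method that adjusts for the pre-test score, and it does not assign any test to a question.

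**The concern.** The questions and the objectives ask different things, and the list of tests serves both. A paired t-test or Wilcoxon test in the PK arm answers whether PK students scored higher after teaching than before. Any teaching on the topic, or simply taking the same test again, could produce that gain, so it says nothing about PK relative to PowerPoint. A two-sample test answers the objective. As worded, a positive paired result would be enough to answer the research questions with a yes, and the randomised comparison would not have been used.

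The second issue is precision. The class size is fixed at 71. The two-sample tests use the post-test or delayed score alone, although a pre-test is collected from the same students and used to stratify. What is at stake is the basis of the main conclusion, and the size of difference that the trial can detect.

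**Working it through.** The Protocol states no power, effect size or SD, so it has no figure to reproduce.

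**Inputs.** From the Protocol: 71 students, level 0.05, three measurements. Assumed: a 36/35 split, two-sided tests, SD of 1 at each time, and equal correlation ρ between any two times of 0.3, 0.5 or 0.7. Each scenario was simulated 10,000 times with simple randomisation.

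**1. What a paired test shows when PK is no better than PowerPoint.** Both arms receive the same true pre-to-post gain. The SD of the change is √(2(1−ρ)), and the standardised gain is d = gain / √(2(1−ρ)). The paired t-test with n = 36 has 35 degrees of freedom and noncentrality d√36. For a gain of 0.5 SD and ρ = 0.5, √(2 × 0.5) = 1, so d = 0.5 and the noncentrality is 0.5 × 6 = 3.0. The power is 0.831 and the simulated value is 0.827, so the two agree.

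| Common gain (SD) | PK paired test significant, ρ = 0.3 / 0.5 / 0.7 | Two-sample test at post-test significant, same ρ |
|---|---|---|
| 0.2 | 17.0% / 20.3% / 32.6% | 5.0% / 4.6% / 5.2% |
| 0.35 | 40.6% / 53.1% / 74.7% | 4.8% / 5.0% / 5.2% |
| 0.5 | 67.9% / 82.7% / 96.5% | 5.4% / 5.1% / 4.9% |
| 0.8 | 97.6% / 99.7% / 100% | 4.9% / 4.9% / 5.2% |
| 1.0 | 99.8% / 100% / 100% | 4.6% / 5.2% / 5.2% |

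The paired test is right that scores rose. It carries no information on whether PK did better than PowerPoint.

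**2. Whether the listed two-sample tests work at the delayed post-test.** With no true difference, the two-sample t-test on the post-test score, the delayed score or the post-to-delayed change was significant in 4.6% to 5.7% of trials. With an assumed 0.7 SD difference that arises only at the delayed test, the t-test on the delayed score has about 83% power (83.9% by formula). The t-test on the change from post-test to delayed test has 69%, 82% and 96% power at ρ = 0.3, 0.5 and 0.7. These are usable, valid randomised comparisons.

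**3. What ignoring the pre-test score costs.** The difference detectable with 80% power, in SD units by normal approximation, is

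(1.960 + 0.842) × √(1/36 + 1/35) = 2.802 × 0.2374 = 0.67.

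Adjustment for a baseline score with correlation ρ multiplies the variance by 1 − ρ²:

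| ρ | 1 − ρ² | Detectable difference (SD) | Unadjusted class size for the same precision, 71/(1 − ρ²) |
|---|---|---|---|
| none | 1 | 0.67 | 71 |
| 0.3 | 0.91 | 0.63 | 78 |
| 0.5 | 0.75 | 0.58 | 95 |
| 0.7 | 0.51 | 0.47 | 139 |

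**The case against.** The best defence is that the sections should be read together. The design is randomised and controlled, both objectives compare the arms, and the between-arm tests that they need are listed. Nothing assigns the paired tests to the research questions. Which test serves which outcome and time point is commonly left to an SAP, which was not available here. Baseline adjustment improves precision; validity does not depend on it. Most of this stands, and it is why the point is an improvement and not a fatal flaw. It does not remove the mismatch, because the wording of the questions is Protocol content.

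Three stronger readings are tempting and are not supported:

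- A reader might infer that the listed tests cannot address retention because each handles only two measurements. A between-arm contrast needs only one score, or one change, per student. A t-test or Mann-Whitney U test on the delayed score or on the post-to-delayed change is valid, as step 2 shows. With two arms, the change-score t-test is equivalent to the group-by-time interaction over those two times.
- A reader might infer that no listed test compares the arms. The t-test and the Mann-Whitney U test do.
- A reader might infer that a difference between arms will be declared when one arm's paired test is significant and the other's is not. That would be an invalid rule, but the Protocol states no such rule, so error rates computed under it should not be held against the plan.

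**Conclusion.** The point holds in this limited form. The research questions omit the comparator that the objectives require, and the listed paired tests leave room to report a within-arm gain as an effect of PK. With equal gains in both arms, such a gain would be significant in about 17% to 33% of trials at 0.2 SD and in 98% or more at 0.8 SD and above. The two-sample tests are sound but give up precision: 0.67 SD detectable without the pre-test score, against 0.63 to 0.47 SD with it.

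The split, SD, correlations, gains and two-sidedness are all assumptions, so the figures show a range and do not predict this trial. The detectable differences also ignore the few degrees of freedom that the covariates use, and assume a roughly linear relation between pre-test and later scores. The label is free improvement.

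**What to change.** 1. Add a comparison with traditional PowerPoint to both research questions, so that they match the objectives.
2. State that conclusions rest on the PK minus PowerPoint difference, with its 95% CI, at the post-test and separately at the delayed post-test, adjusted for pre-test score and gender. Gender belongs in the model because it is also a stratification factor. Either an ANCOVA at each time or a mixed model with group, time, group-by-time, pre-test score and gender will do. Retention is then read from the group contrast at the delayed post-test.
3. Report paired within-arm changes descriptively, and do not use them to support a claim that PK improves an outcome.

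The cost is a rewording of Research Questions and Data Analysis. The pre-test score and gender are already collected, and no extra students, visits or staff are needed.

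### The named between-group tests leave the pre-test score and gender unused, which gives up precision in a class capped at 71 students

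*Protocol*

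**What the plan says.** Study Design: "A randomized controlled experimental design with pre- and post-test measurements will be employed".

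Population and Sample: "The population consists of 71 second-year nursing students enrolled in the Surgical Nursing course". Students are allocated "using block randomization based on pre-test scores (≤ 60 / > 60) and gender (female/male").

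Data Collection fixes the order: "Pre-test conducted one week prior to lecture; block randomization follows". A post-test and a delayed post-test come after the teaching session.

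Study Objectives: the first is to "Determine differences in cardiovascular ERAS knowledge levels between students educated via Pecha Kucha versus traditional PowerPoint". The second makes the same comparison between groups for attitudes toward evidence-based nursing.

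Data Analysis: "Descriptive statistics, t-tests, Mann-Whitney U, paired t-tests, Wilcoxon, Chisquare", then "Significance at $p < 0.05". No ANCOVA, regression or stratified test is listed. The Protocol states no sample-size calculation, power, effect size, SD or pre/post correlation.

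**The concern.** Both objectives are comparisons between arms. Among the listed methods for scores, only the two-sample t-test and Mann-Whitney U make that comparison, and neither uses the pre-test score or gender. The paired t-test and Wilcoxon test describe change within an arm and do not answer either objective.

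Stratifying on the pre-test makes sense only if it is expected to predict the outcome. If it does, leaving it out of the analysis has two consequences.

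- **Lost precision.** Variation in the post-test that the pre-test could explain stays in the error term. Pre-test differences within the two broad categories, and in any scale not used for stratification, are left to chance. With one class of 71, more students cannot make up the loss.
- **A standard error that may be too large.** The t-test computes its standard error as if allocation were unrestricted. If the strata predict the outcome, the estimate varies less than that standard error says, and the test is conservative.

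**Working it through.** There is no sample-size figure in the Protocol to reproduce, so the check asks what adjustment would gain.

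**Inputs**
- From the Protocol: 71 students; significance level 0.05; pre-test before randomisation; strata of pre-test ≤ 60 / > 60 by gender.
- Assumed: a 35 versus 36 split, a two-sided test, a true difference of 0.5 SD, and a pre/post correlation r between 0 and 0.7.

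**Step 1: power and smallest detectable difference**

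In SD units the unadjusted standard error is √(1/36 + 1/35) = 0.237. A difference of 0.5 SD gives a noncentrality of 0.5/0.237 = 2.11 and, on 69 degrees of freedom, power of 55%. The difference detectable with 80% power is 0.674 SD.

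ANCOVA on the pre-test multiplies the standard error by √(1 − r²). The detectable difference shrinks by the same factor, and the unadjusted sample of equal precision is 71/(1 − r²).

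| r | SE factor | Power at 0.5 SD | Detectable difference, 80% power | Equivalent unadjusted N |
|---|---|---|---|---|
| 0 (unadjusted) | 1.00 | 55% | 0.67 SD | 71 |
| 0.1 | 0.995 | 55% | 0.67 SD | 72 |
| 0.3 | 0.954 | 59% | 0.64 SD | 78 |
| 0.5 | 0.866 | 67% | 0.58 SD | 95 |
| 0.7 | 0.714 | 83% | 0.48 SD | 139 |

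A t-test on change scores would not be a substitute. Its standard error factor is √(2 − 2r), which is 1.18 at r = 0.3 (worse than ignoring the pre-test), 1.00 at r = 0.5 and 0.77 at r = 0.7. ANCOVA has the smaller factor at each of these values.

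**Step 2: is the t-test's standard error too large after stratification?**

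Take a normally distributed pre-test cut so that a proportion p lies below the cut-off. The share of pre-test variance captured by the category is k = φ(z)²/[p(1 − p)], where z is the cut-off in SD units. With balanced strata, the true SD of the estimate is about √(1 − r²k) times the reported standard error, and the true size is about 2[1 − Φ(1.96/√(1 − r²k))].

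- Cut-off at the median: k = 0.399²/0.25 = 0.637. At r = 0.5 the ratio is √(1 − 0.25 × 0.637) = 0.917 and the size 3.3%. At r = 0.7 the ratio is 0.830 and the size 1.8%. At r = 0.3 the size is 4.4%.
- Cut-off at the 90th percentile: k = 0.1755²/0.09 = 0.342. The sizes are 4.7%, 4.0% and 3.2% at r = 0.3, 0.5 and 0.7.

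Simulations used 71 students, permuted blocks of 4 within pre-test category by gender, and at least 6,000 trials per setting where the count was recorded. Runs with and without a small gender effect agreed with the formula:

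| Where 60 falls | Size of t-test, r = 0.5 | Size of t-test, r = 0.7 |
|---|---|---|
| Median | 2.7–3.2% | 2.0–2.2% |
| 90th percentile | 4.0–4.6% | 3.2–3.6% |
| 97th percentile | 4.8% | 4.6% |
| No student above 60 | 5.0% | 5.1% |

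At r = 0.3 the simulated size was between 4.3% and 5.4% at every cut-off. ANCOVA on the continuous pre-test and gender kept its size between 4.6% and 5.5%. Its simulated power matched Step 1 (67% at r = 0.5 and 83% at r = 0.7) whether the cut-off sat at the median or at the 90th percentile.

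**The case against.** **The listed tests are valid.** This stands. A two-sample comparison is unbiased over the randomisation, and its size is at or below the nominal level. A positive result would hold, and the Protocol states no power target that the choice breaks. A reader might infer that the planned analysis is wrong or would mislead; the documents support only that it is less efficient than it could be.

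**The gain may be small.** This stands as a limit on the size. The Protocol gives no correlation, and its background section reports low ERAS awareness even among practising nurses. If students' pre-test knowledge scores cluster low, the correlation could be weak and the gain near zero. At r = 0, however, adjustment costs almost nothing.

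**Error bars that are too wide throughout would be an overstatement.** This also stands. The strong figures of about 2 to 3% need 60 to fall near the class median. If few students exceed 60, the distortion nearly disappears. The cut-off suits the 100-point knowledge test, and nothing in the Protocol shows that this category predicts attitude, so the conservatism should not be assumed for the second objective.

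**A data-driven switch of target is not stated.** Seeing both a t-test and Mann-Whitney U, a reader might infer that the quantity estimated will change with the data. The Protocol names both but gives no rule for choosing, so that cannot be held against it.

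**The SAP may add adjustment.** The list is terse and does not say it is exhaustive, so a later plan could extend it. That does not dispose of the point: the Protocol itself names the tests, and every between-group test it names is unadjusted.

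**Conclusion.** The point holds as a loss of precision. It should be fixed, and doing so is a free improvement; it is not an error that threatens validity. For a true difference of 0.5 SD the loss runs from nothing at a correlation near 0.1, through about 4 points of power at 0.3 and 12 at 0.5, to 28 at 0.7. These figures rest on a near-equal split, a two-sided 5% test and complete data on all 71 students. The conservatism of the t-test is a secondary effect, argued here for the knowledge score only, and depends on how the cut-off of 60 divides the class and how well it predicts the post-test.

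**What to change.** In Data Analysis, make the between-group analysis of each outcome (knowledge and attitude), at post-test and at delayed post-test, an ANCOVA of the score on arm, the continuous pre-test score of the same scale, and gender. Add the pre-test stratum if both categories are populated. Report the adjusted mean difference with its 95% confidence interval, with robust or bootstrap standard errors if residuals are clearly non-normal. Keep Mann-Whitney U as a sensitivity analysis and the paired tests as description within arms.

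The cost is a few sentences. The covariates are already to be collected, the named software fits the model, and no extra students are needed. The change should be made before outcome data are seen, so that the adjustment cannot be taken for a data-driven choice.

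### The protocol applies p < 0.05 to two unranked objectives and two follow-up tests without naming a primary outcome, time point or comparison

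*Protocol*

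**What the plan says.** Study Objectives in the protocol lists two aims, both comparing the arms. The first is "Determine differences in cardiovascular ERAS knowledge levels between students educated via Pecha Kucha versus traditional PowerPoint". The second is "Assess differences in attitudes toward evidence-based nursing between these groups". Neither is labelled primary or secondary. Research Questions puts the same two topics differently: it asks whether education given by PK improves knowledge and improves attitudes, and mentions no comparator.

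Data Collection Tools describes the attitude instrument as "15-item Likert scale, 3 subscales: beliefs and expectations, implementation intention, emotions". Data Collection sets two follow-up measurements: "Post-test and delayed post-test conducted to assess retention". It does not say which instruments are repeated at the delayed test.

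Data Analysis lists the methods as "Descriptive statistics, t-tests, Mann-Whitney U, paired t-tests, Wilcoxon, Chisquare", followed by the single criterion "Significance at $p < 0.05". That list mixes between-group tests with within-group tests (paired t-test, Wilcoxon) and does not tie any test to an objective or a time point.

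**The concern.** A reader of the finished trial needs to know which single result was to decide whether PK works better than PowerPoint. The protocol does not say. Knowledge or attitude, at the post-test or the delayed test, could each be put forward once the results are known, each judged at 0.05 as if it were the only one. The error rate attached to the statement that PK had an effect is then above 5%, and nobody can say by how much, because the number of tests is open as well.

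There is a second route to a claim. Research question 1 has no comparator, and paired tests are listed under the same threshold. A significant pre-post gain in the PK arm alone could be offered as a yes to that question. Students can be expected to score higher after any lecture on the topic, so such a gain would not show that PK did better than PowerPoint.

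**Working it through.** **Inputs from the protocol.** Threshold 0.05 per test (Data Analysis; sidedness not stated, two-sided assumed). Two objectives (Study Objectives). Three attitude subscales (Data Collection Tools). Two follow-up times (Data Collection). 71 students (Population and Sample).

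**Assumptions.** Arms of 36 and 35, with all 71 taking part. One test per comparison. PK has no effect on anything. Within-arm tests are left out of the count, because gains are expected in both arms and do not test PK against PowerPoint. The protocol states no familywise error, power or effect size, so there is no figure of its own to reproduce.

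**Step 1: independent tests.** For k tests at 0.05, the chance of at least one false positive is 1 − 0.95^k.

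| What is tested between groups | k | 1 − 0.95^k |
|---|---|---|
| Two outcomes, one time | 2 | 9.75% |
| Two outcomes, two times | 4 | 18.5% |
| Knowledge at two times; attitude total and 3 subscales once | 6 | 26.5% |
| Knowledge and 3 subscales, two times | 8 | 33.7% |
| Knowledge, attitude total and 3 subscales, two times | 10 | 40.1% |

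Only the first row needs no assumption about repeated attitude measurement or separate subscale tests. The four-test row assumes that attitude is measured again at the delayed test. The ten-test row assumes that too, and also that each subscale is tested separately beside the total.

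**Step 2: correlated tests.** The scores come from the same students, so independence overstates the figures. Two models were tried.

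- One common correlation among all test statistics (200,000 simulated runs). At correlations 0.3, 0.5 and 0.7, four tests give 17.6%, 15.7% and 13.0%; ten tests give 34.8%, 28.7% and 21.3%.
- A structured model: two-sample t-tests on 36 versus 35 students, 10,000 runs, attitude total equal to the sum of its subscales, correlation 0 to 0.7 between times and among subscales, and 0 or 0.2 between knowledge and attitude. Four tests give about 16-19%, six 19-24%, eight 25-34%, ten 25-37%.

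Taken together, the ranges are about 13-19% for four tests and 21-37% for ten. The 40.1% is a ceiling for the ten-test case, because a total built from its subscales cannot be independent of them.

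**Step 3: effect of fixing the rule.** One named comparison at 0.05 carries a 5% error. Two primary tests at 0.025 carry at most 0.025 + 0.025 = 5%, against 9.75% unadjusted. The cost of the split is in sensitivity: with 35 and 36 students, the true difference detectable with 80% power rises from 0.666 to 0.732 standard deviations (0.732 / 0.666 = 1.10, about 10% larger).

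**The case against.** The strongest reply has three parts.

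First, the two objectives are separate questions. A significant attitude result answers the second and not the first, and with one score at one time each claim carries its own 5% error. Whether distinct questions need joint control is a matter of debate. This stands as far as it goes, but it does not settle which time point or which comparison answers either question. Knowledge being listed first does not settle it either, since nothing in the protocol makes it primary.

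Second, adjustment for multiplicity, testing order and the handling of subscales commonly sit in a statistical analysis plan, which is not shown here. That is right, and the absence of an adjustment method is not the point made. Which outcome, when, and against what is protocol content.

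Third, the test count could be read too generously. A reader might infer that the protocol tests the attitude total and each subscale at both follow-up times. It does not say so: the subscales appear only in the description of the instrument, the second objective speaks of attitudes as a whole, and retention may well refer to the knowledge test alone. This objection stands, and the larger counts are scenarios only.

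**Conclusion.** The point holds in a limited form. The protocol sets one flat threshold over two unranked objectives, two follow-up times and a mix of between-group and within-group tests, and names no primary outcome, time point or comparison. On the narrowest reading, the chance of a false-positive PK versus PowerPoint result is about double the nominal 5%. On the widest it is up to 40%. The figures rest on there being no true effect, on the assumed correlations, and, beyond two tests, on testing that the protocol leaves unstated.

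Two stronger readings are not supported. A reader might conclude that a false positive is likely. None of the scenarios reaches 50%, and even independent tests would pass that mark only at 14 (1 − 0.95^14 = 51.2%), more than the scores and times described provide for. A reader might also call the two outcomes co-equal by design; the protocol only leaves them unranked.

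**What to change.** Before registration, which Study Design places ahead of the start of the study, add one of the following to the protocol. The choice of outcome and time point belongs to the investigators.

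- **One primary comparison.** PK versus PowerPoint on one outcome at one time point, at two-sided 0.05; for example, total cardiovascular ERAS knowledge score at the immediate post-test. Label attitude and the other time point as secondary and test them in a stated fixed order, stopping at the first non-significant result.
- **Two primary comparisons.** If both objectives are meant as primary, test each between groups at 0.025 at one named time point.

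In either case, state whether attitude is measured at the delayed test. Report subscales and within-arm changes as estimates with 95% confidence intervals, not as evidence of a PK effect. Reword the research questions so that they carry the PowerPoint comparator already in the objectives.

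The cost is a few sentences. Under the fixed order, later outcomes cannot be claimed if an earlier one fails. Under the split, each primary test has somewhat less power.
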